8. RISKS/PRECAUTIONS

8.1 IV Iron Risks

Parenterally administered iron preparations can cause hypersensitivity reactions including anaphylactoid reactions, which may be fatal. Therefore, facilities for cardiopulmonary resuscitation must be available. If allergic reactions or signs of intolerance occur during administration, the treatment must be stopped immediately. Hypersensitivity reactions have been reported after previously uneventful doses of any parenteral iron complexes, including FCM. Each subject should be observed for adverse effects for at least 30 minutes following administration of the study treatment.

In subjects with liver dysfunction, parenteral iron should only be administered after careful benefit/risk assessment. Parenteral iron administration should be avoided in subjects with hepatic dysfunction where iron overload is a precipitating factor, in particular porphyria cutanea tarda. Careful monitoring of iron status is recommended to avoid iron overload.

Parenteral iron must be used with caution in cases of acute or chronic infection, asthma, eczema or atopic allergies. It is recommended that the administration of FCM be stopped in subjects with ongoing bacteraemia. In subjects with chronic infection, a benefit/risk evaluation has to be performed, taking into account the suppression of erythropoiesis (due to chronic infection).

Paravenous leakage must be avoided because leakage of FCM solution at the injection site may lead to irritation of the skin and potentially long-lasting, brown discolouration at the site of injection. In the event of paravenous leakage, administration of FCM must be stopped immediately. Study treatment administration may be completed using a different injection site to complete the required dosage.

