10.3 Reporting Procedure for AEs, SAEs and Pregnancy

10.3.1 Adverse Events

All AEs either observed by the Investigator or one of his/her medical collaborators, or reported by the subject spontaneously, or in response to a direct question, will be noted in the AE section of the subject's eCRF and source documentation. This applies to all AEs regardless of presumed relationship to the study. AEs leading to discontinuation of study treatment should also be collected.

If any AE is reported, the date of onset, relationship to study treatment, any action taken, date of resolution (or the fact that it is still continuing or has become chronic), outcome, intensity (worst at any point during the event) and whether the AE was serious or not at any time during the event will be recorded. In order to establish the duration of any SAE, the dates of hospitalisation and discharge or dates of meeting other SAE criteria will be recorded in the eCRF.

Where possible, the Investigator should report a diagnosis rather than individual signs and symptoms or abnormal laboratory values. However, if a constellation of signs and/or symptoms cannot be medically characterised as a single diagnosis or syndrome at the time of reporting, each individual event should be recorded in the eCRF. If a diagnosis is subsequently established, all previously reported AEs based on signs and symptoms should be nullified and replaced by 1 AE report based on the single diagnosis, with a starting date that corresponds to the starting date of the first symptom of the eventual diagnosis.

The Investigator should use standard medical terminology/concepts; avoid colloquialisms and abbreviations. Only 1 AE term should be recorded in each event field in the eCRF.

The AE reporting period begins at the time the ICF is signed by the subject. The AE reporting period ends at the last study/follow-up visit (Week 52 – Visit 6).

AEs that extend continuously, without resolution, between trial assessments should only be recorded once in the eCRF. The initial severity of the event should be recorded, and the severity should be updated to reflect the most extreme severity any time the event worsens.

AEs that resolve and subsequently recur should have each recurrence recorded separately in the eCRF.

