2.5.4. Safety Endpoints

- Incidence of adverse events (AEs): by System Organ Class (SOC) and Preferred Term (PT) (Medical Dictionary for Regulatory Activities (MedDRA) coded term), by maximum severity, related to study drug, leading to study drug discontinuation, serious, leading to death, and adjudicated.
- Incidence of AEs of clinical interest: HF hospitalisation and CV death.
- Incidence of Special Situation Events.
- Incidence of event adjudication (Hospitalisation, Urgent HF visit and Deaths).
- Incidence of related AEs of special interest: Hypersensitivity reactions, Hypophosphatemia, Injection/infusion site reactions and Haemosiderosis.
- Clinical laboratory panels (absolute and change from baseline, incidence of laboratory abnormalities).
- Vital Signs (absolute and change from baseline).
- Electrocardiograms (incidence of electrocardiogram abnormalities, QTc measurement meeting ICH E14 criteria [2]).
- Prior, concomitant and newly started medications.

Note: biomarkers exploratory analyses will not be part of the CSR of the main study. They will be described in a separate biomarker SAP.

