2. For CV death: SOC = “Cardiac Disorders” and results in death = Yes, and PT=”Sudden cardiac death” in SOC “General disorders and administration site conditions”

AEs of special interest include “hypersensitivity reactions”, “hypophosphatemia”, “injection/infusion site reactions” and “haemosiderosis”. Only events related to study drug are considered. Each category will be identified as follows:

1. Hypersensitivity reactions: PT = “Hypersensitivity”, “Anaphylactic reaction”, “Anaphylactic shock”, “Anaphylactoid shock” or “Anaphylactoid reaction”
2. Hypophosphatemia: PT = “Blood phosphorus decreased”, “Blood phosphorus abnormal”, “Hypophosphataemia”, “Hypophosphataemic osteomalacia” or “Hereditary hypophosphataemic rickets”
3. Injection/infusion site reactions: HLT = “Infusion site reaction”, “Injection site reactions”, “Administration site reactions NEC” or “Infusion related reaction”
4. Haemosiderosis: PT = “Haemosiderosis”, “Haemeatochromatosis”, “Iron overload”, “Hepatic siderosis”, “Cardiac iron overload”, “Pulmonary haemosiderosis” or “Superficial siderosis of central nervous system”

A listing of pre-study AEs and listing of AEs starting between randomisation date and start of treatment will be presented. All TEAEs occurring on study will be listed in subject data listings, as will related TEAEs, SAEs, related SAES, TEAEs leading to study drug discontinuation or death. Data will not be imputed in the listings.

Relevant pregnancy information captured in the eCRF will be listed.

All deaths details will be listed.

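### The hypersensitivity event of special interest is searched by five umbrella preferred terms, so a drug-related reaction recorded as separate signs is missed in that category

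*SAP*

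**What the plan says.** SAP section 2.5.4 makes the category a safety endpoint: "Incidence of related AEs of special interest: Hypersensitivity reactions, Hypophosphatemia, Injection/infusion site reactions and Haemosiderosis". SAP section 4.8.2 then sets the search. It opens with "Only events related to study drug are considered. Each category will be identified as follows", and the hypersensitivity line reads "Hypersensitivity reactions: PT = “Hypersensitivity”, “Anaphylactic reaction”, “Anaphylactic shock”, “Anaphylactoid shock” or “Anaphylactoid reaction". The results go to one row of the adverse event overview (Table 14.3.1.1) and to Table 14.3.1.17. Listing 16.2.7.5 is also titled for hypersensitivity reactions, but the SAP does not say how its entries are selected.

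The protocol describes the risk in wider terms. Section 8.1 says "Parenterally administered iron preparations can cause hypersensitivity reactions including anaphylactoid reactions, which may be fatal", and adds "If allergic reactions or signs of intolerance occur during administration, the treatment must be stopped immediately". Section 5.4.1 likewise speaks of related hypersensitivity reactions of every kind.

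On recording, protocol section 10.3.1 prefers a diagnosis to individual signs where one can be made. Where the signs cannot be put together as one diagnosis or syndrome when the report is made, "each individual event should be recorded in the eCRF". If a diagnosis is reached later, it replaces the sign-level entries.

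**The concern.** For an event of special interest, the term list is the endpoint definition. Four of the five terms are anaphylactic or anaphylactoid, and the fifth is the general term Hypersensitivity. There is no sign-level term such as urticaria, angioedema, bronchospasm or rash, and no high-level term, organ class or standardised query behind the list. A reaction that the protocol would regard as hypersensitivity, and that the investigator judges related, can therefore fall outside the row meant to count it.

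What is at stake is one safety summary: the number of subjects per arm with a hypersensitivity-type reaction, which is a risk the protocol names prominently for intravenous iron. No efficacy result and no formal test depends on it.

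**Working it through.** The plan states no expected rate, power or other figure for this category, so there is nothing to reproduce. The check is to set the rules side by side and follow one subject through them.

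**1. Scope of the concept.** Protocol section 8.1 treats anaphylactoid reactions as one part of hypersensitivity and refers also to allergic reactions and signs of intolerance. Section 5.4.1 sets no lower limit on the kind of reaction. The five-term list covers the severe end and the umbrella diagnosis only.

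**2. Recording.** Under protocol section 10.3.1, a reaction with no single diagnosis is entered as its component signs. Each entry is coded to its own preferred term.

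**3. Comparison within SAP section 4.8.2.** The other three categories are searched more inclusively. Injection and infusion site reactions are searched by high-level term. Hypophosphataemia includes laboratory-finding terms as well as diagnoses. Haemosiderosis includes several organ-specific terms. Hypersensitivity alone has neither a grouping term nor a sign-level term.

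**4. One subject traced through the tables.** Suppose a subject has urticaria and bronchospasm after an injection, both judged related, entered as two events with no diagnosis made later, and no other special-interest event.

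| Output | Contribution of this subject |
|---|---|
| Special-interest row of the overview | 0 |
| Hypersensitivity category of Table 14.3.1.17 | 0 |
| Related events by class and term (Table 14.3.1.3) | 1 in the urticaria row and 1 in the bronchospasm row |

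SAP section 4.8.2 counts a subject once within a given class or term, but not across terms. Adding the two rows gives 1 + 1 = 2 for one subject. The number of affected subjects per arm therefore cannot be recovered by adding rows of the general tables.

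**5. The listing.** Listing 16.2.7.5 might show such a subject, but without a selection rule that cannot be assumed. A listing is also not an incidence by arm.

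**The case against.** The strongest reply is that little is hidden. Reactions recorded as signs are tabulated by arm in Tables 14.3.1.2 and 14.3.1.3 and, if serious, in Tables 14.3.1.7 and 14.3.1.10. Related events are also listed by subject. That stands: a reader might infer that these reactions vanish from the report, and they do not. What remains is that no planned output counts the affected subjects as a group.

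Secondly, the recording rule prefers a diagnosis, and urticaria with bronchospasm during an iron injection is a case where an investigator may well write hypersensitivity, which is on the list. Section 5.4.1 also requires a judgement about hypersensitivity when a reaction occurs during administration. Some other reactions may fall in the infusion and injection site category. This stands too, and it limits the gap. It does not close it, because section 10.3.1 provides for the case where no diagnosis is made.

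Thirdly, a reader might infer a sizeable under-count, or a known bias toward no difference between the arms. The documents do not support either. They give no hypersensitivity rate, and protocol section 8.2 does not name hypersensitivity among the reactions seen in 1% to 10% of subjects. Exclusion criteria 11 and 12 remove many subjects at higher risk. With saline as comparator it is plausible that missed true reactions would lie mostly on ferric carboxymaltose, but that is reasoning, not a figure in the plan.

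Two neighbouring lines of section 4.8.2 also invite stronger readings than they bear:

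- The iron-overload search, "Haemosiderosis: PT = “Haemosiderosis”, “Haemeatochromatosis”, “Iron overload", contains a misspelt term. To say that haemochromatosis would never be found assumes a literal text match, which the SAP does not specify. The slip is clerical.
- The rule that begins "For CV death: SOC = “Cardiac Disorders” and results in death = Yes" goes on to join a term from a second organ class with the word and. Taken literally, no event coded to a single class could qualify, but the text is evidently a two-item list. The rule omits fatal strokes and emboli coded to other classes. However, the row is described as investigator-reported, section 4.8.4 tabulates adjudicated causes of death in the safety set, and the efficacy endpoints use adjudicated deaths. It is a labelling point.

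**Conclusion.** The five-term search is narrower than the protocol's concept of hypersensitivity and can under-count affected subjects in the special-interest overview row and Table 14.3.1.17. This follows from the documents' own definitions and recording rule. It assumes only that at least some related reactions are entered as signs without a diagnosis made later.

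The size cannot be derived from the documents. It is bounded by the preference for a diagnosis, and the events remain visible by class and term elsewhere. The primary and secondary efficacy results are unaffected. The change is worth making because it concerns a named safety endpoint and is cheap. The spelling and the cardiovascular death wording are minor notes only.

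**What to change.** In SAP section 4.8.2:

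- Add a hypersensitivity row by arm, counting each subject once, that uses the standardised MedDRA queries for hypersensitivity (narrow) and anaphylactic reaction.
- Keep the five-term list as a subset row, so that the present definition is still reported.
- Show onset on the day of an injection or the day after as an additional breakdown. It should not be a filter, since as the only count it would drop later reactions.
- Apply the same selection to Listing 16.2.7.5, and state it.

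Minor wording: correct the spelling of the haemochromatosis term; replace the joining and with or in the CV-death rule; label that row as investigator-reported cardiac death, with a reference to the adjudicated cause-of-death table (14.4.1.1).

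The cost is SAP wording and a revised term search on data that are already to be coded in MedDRA, with no new data collection. The downside is that the wider search will admit a few unrelated skin or respiratory events in both arms. The retained five-term row and the onset breakdown let the reader see how much that matters.

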4.8.3. Special Situations

Special situations collected in the eCRF will be listed.

The following special situations will be reported by category and preferred term:

- Pregnancy or breastfeeding
- Medication abuse
- Medication error
- Medication misuse
- Medication overdose
- Occupational exposure: *defined as an exposure to a medicinal product for human use as a result of one's professional or non-professional occupation*
- Drug interaction
- Unexpected therapeutic or clinical benefit

4.8.4. Event Adjudication

Details on adjudications performed by the CEC will be tabulated for the SAF analysis set. The number of events adjudicated and the adjudication decisions will be summarised by treatment group, along with the number of hospitalisations adjudicated, the number of urgent HF visits (including emergency room and unscheduled outpatient visits), and the number of deaths adjudicated with cause of death.

Adjudication information will also be listed.

4.8.5. Laboratory Data

Laboratory data, including haemoglobin (g/dL), serum ferritin (ng/mL), transferrin saturation (%), and phosphorus (mg/dL), are assessed at Screening, Week 6, Week 12, Week 24, and Week 52 (except for pregnancy tests). Please see Appendix III for a description of parameter, unit and number of decimals to be displayed in summary tables.

The actual value and change from baseline to each on-study evaluation will be summarised for each parameter at each scheduled visit, as well as for the last available post-baseline value (see section 4.2.16). Determination of baseline for all endpoints is described in section 4.2.12. For all post-baseline time points, the windowing described in section 4.2.9 will be applied.

Categorical shift tables from baseline to all visits will also be presented, showing the numbers of subjects with values outside the normal ranges as reported on the eCRF (categories Normal, Abnormal Non-Clinically Significant, Abnormal Clinically Significant).

Additionally, a shift table from baseline to all visits and to the lowest post-baseline value will be presented for phosphorus. Categories included in this shift table are: < 1 mg/dL, 1-< 2 mg/dL, 2-< 2.5 mg/dL, 2.5-< 4.5 mg/dL and >= 4.5 mg/dL.

The value of eGFR will be computed using CKD-EPI formula:

$$\text{eGFR (mL/min/1.73m}^2\text{)} = 141 \times \min(S_{\text{cr}}/\kappa, 1)^\alpha \times \max(S_{\text{cr}}/\kappa, 1)^{-1.209} \times 0.993^{\text{age}} \times 1.018 \text{ [if female]} \\ \times 1.159 \text{ [if black]},$$

where

S_{cr} is serum creatinine in mg/dL,
 κ is 0.7 for females and 0.9 for males,
 α is -0.329 for females and -0.411 for males,
age at baseline is used.

All laboratory data including screening laboratory values (creatinine, eGFR, BNP and NT-proBNP) will be provided in data listings.

Pregnancy test results will be reported in a listing only.

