9.2.3.11 Laboratory Tests Mandated by the Study Protocol

The laboratory tests mandated by the trial protocol to be transferred into the eCRF will be analysed locally. The assays to be performed are Hb, serum ferritin, TSAT, serum phosphorus and serum pregnancy tests in females of childbearing potential.

If available in the subject clinical records within the Index hospitalisation, the latest serum creatinine value measured before randomisation visit will be collected.

Iron status blood test reports and serum phosphorus levels received after randomisation must be provided directly to the unblinded Investigator. This person must enter the results in the eCRF page provided for this purpose.

In addition, blood samples for biomarkers will be taken in a subset of subjects. The baseline biomarker blood sample will be drawn just prior to the injection of study treatment. Blood samples will be stored for up to three years after the end of the trial for future analyses of biomarkers of scientific interest. Details concerning the blood samples storage will be provided in an instruction manual and results of these exploratory analyses will be not part of the clinical study report of the main study.

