4.5.2. Baseline Disease Characteristics

Baseline disease characteristics will include:

- 1) History of cardiovascular risk factors:
 - any risk factor,
 - smoking,
 - hypertension,
 - dyslipidaemia,
 - diabetes mellitus,
 - atrial fibrillation,
 - myocardial infarction,
 - angina pectoris,
 - stroke,
 - coronary revascularization,
 - chronic kidney disease.
- 2) Index hospitalisation information (screening acute heart failure):
 - aetiology (ischaemic, non-ischaemic, unknown; if non-ischaemic, hypertensive, valvular, idiopathic, congenital, other),
 - AHF duration (newly diagnosed at Index hospitalisation, known documented HF prior to Index hospitalisation),
 - time since initial diagnosis to screening (years) as a continuous variable only for those with known HF prior to Index hospitalisation,
 - acute heart failure in the previous 12 months prior to Index hospitalisation (Yes/No),
 - number of hospitalisations in the 12 months prior to screening (for subjects with at least one previous hospitalisation before screening).
- 3) Symptoms and signs of heart failure at time of Index hospitalisation:
 - dyspnoea on exertion,
 - dyspnoea at rest while sitting,
 - orthopnoea and paroxysmal nocturnal dyspnoea,
 - peripheral oedema,
 - pulmonary congestion (crackles, rales),
 - liver enlargement,
 - presence of a third heart sound (S3 gallop),
 - jugular venous distension,
 - jugular venous measurement (cm).

- 4) Other baseline disease characteristics:
- left ventricular ejection fraction (%), left ventricular ejection fraction as categorical variable (<40%, 40-<50%, >=50%)
 - New York Heart Association Classification (Class I, II, III, IV),
 - baseline weight (kg), height (cm), BMI (kg/m²) and temperature (°C),
 - baseline laboratory data: haemoglobin (g/dL), haemoglobin as categorical variable (<10, 10-14, >14), anaemic/non-anaemic subjects (anaemic: adult males with Hb < 13 g/dL, adult females, non-pregnant with Hb <12), serum ferritin (ng/mL), serum ferritin as categorical variable (<100, 100-<300, >=300 ng/mL), transferrin saturation (%), transferrin saturation as categorical variable (<20%, >=20%), phosphorus (mg/dL), phosphorus as categorical variable (<1, 1-<2, 2-<2.5, 2.5-<4.5, >=4.5), creatinine (mg/dL), Brain natriuretic peptide (BNP) (pg/mL), N-terminal-probrain natriuretic peptide (NTproBNP) (pg/mL).

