		14.4.2.1 Summary of Special Situation Events – Safety Analysis Set
		14.4.3.1.1 Laboratory Values: Actual Values and Changes from Baseline by Analysis Visit for Serum ferritin (ng/mL) – Safety Analysis Set
		14.4.3.1.2 Laboratory Values: Actual Values and Changes from Baseline by Analysis Visit for Haemoglobin (g/L) – Safety Analysis Set
		14.4.3.1.3 Laboratory Values: Actual Values and Changes from Baseline by Analysis Visit for Transferrin saturation (%) – Safety Analysis Set
		14.4.3.1.4 Laboratory Values: Actual Values and Changes from Baseline by Analysis Visit for Phosphorus (mg/dL) – Safety Analysis Set
		14.4.3.2.1 Shift from Baseline and Post-Baseline Analysis visits for Normal versus Abnormal Laboratory Values for Serum ferritin (ng/mL) – Safety Analysis Set
		14.4.3.2.2 Shift from Baseline and Post-Baseline Analysis visits for Normal versus Abnormal Laboratory Values for Haemoglobin (g/L)– Safety Analysis Set
		14.4.3.2.3 Shift from Baseline and Post-Baseline Analysis visits for Normal versus Abnormal Laboratory Values for Transferrin saturation (%) – Safety Analysis Set
		14.4.3.2.4 Shift from Baseline and Post-Baseline Analysis visits for Normal versus Abnormal Laboratory Values for Phosphorus (mg/dL) – Safety Analysis Set
		14.4.3.3 Shift from Baseline and Post-Baseline Analysis visits and Lowest Post-Baseline Value for Phosphorus (mg/dL) – Safety Analysis Set
		14.4.4.1.1 Vital Signs: Actual Values and Changes from Baseline by Analysis Visit for Height (cm)– Safety Analysis Set
		14.4.4.1.2 Vital Signs: Actual Values and Changes from Baseline by Analysis Visit for Weight (kg)– Safety Analysis Set

Type*	Section	Title
		14.4.4.1.3 Vital Signs: Actual Values and Changes from Baseline by Analysis Visit for Systolic blood pressure (mmHg) – Safety Analysis Set
		14.4.4.1.4 Vital Signs: Actual Values and Changes from Baseline by Analysis Visit for Diastolic blood pressure (mmHg)– Safety Analysis Set
		14.4.4.1.5 Vital Signs: Actual Values and Changes from Baseline by Analysis Visit for Heart rate (beats/min) – Safety Analysis Set
		14.4.4.1.6 Vital Signs: Actual Values and Changes from Baseline by Analysis Visit for Pulse (beats/min) – Safety Analysis Set
		14.4.4.1.7 Vital Signs: Actual Values and Changes from Baseline by Analysis Visit for Temperature (°C) – Safety Analysis Set
		14.4.5.1 Electrocardiogram: Shifts from Baseline and Week 52 Visit for Overall Interpretation – Safety Analysis Set

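### The ferritin and TSAT shift tables carry no low/high direction, so a low-to-high move can look like no change, and no planned table counts persisting iron deficiency or ferritin >=300 ng/mL by arm and visit

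*SAP*

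**What the plan says.** SAP 4.8.5 plans categorical shift tables from baseline to all visits, judged against the normal ranges recorded on the eCRF, using the "categories Normal, Abnormal Non-Clinically Significant, Abnormal Clinically Significant". One category set serves every laboratory parameter. The output list in SAP 7.1 carries it through: Table 14.4.3.2.1 is the ferritin version, and Table 14.4.3.2.3 is described as "Normal versus Abnormal Laboratory Values for Transferrin saturation".

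Phosphorus is treated differently: "Additionally, a shift table from baseline to all visits and to the lowest post-baseline value will be presented for phosphorus". That table uses five value bands.

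Bands for the iron markers already exist. SAP 4.5.2 has "serum ferritin as categorical variable (<100, 100-<300, >=300 ng/mL" and splits TSAT at 20%, but only to describe baseline. Cut-points at 100 ng/mL and 20% also define subgroups in SAP 4.2.6.

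On who sees the results, Protocol 9.2.3.11 states: "Iron status blood test reports and serum phosphorus levels received after randomisation must be provided directly to the unblinded Investigator". Protocol 6.2 makes the unblinded physician responsible for evaluating post-baseline iron values.

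SAP 2.5.4 names the incidence of laboratory abnormalities as a safety endpoint. Protocol 12.8 includes iron status among the safety laboratory panels and asks for shift tables.

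**The concern.** For ferritin and TSAT the intended effect and the possible harm lie in opposite directions on one scale. Subjects start deficient, treatment moves them up, and Protocol 8.1 advises monitoring of iron status so that overload is avoided. A table that records only whether a value is abnormal cannot separate a subject who stayed low from one who went from low to high.

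The split within the abnormal class does not help. Clinical significance is a judgement, not a numeric rule, and after randomisation it appears to be made by someone who knows the allocation. The normal ranges are those of local laboratories, whereas the study's definition of iron deficiency uses fixed cut-offs.

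At stake is whether the clinical study report can state, for each arm and visit, how many subjects remained iron deficient and how many passed the upper ferritin bound of that definition.

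**Working it through.** The plan gives no figure to reproduce. The check sets the category scheme against the transitions it must display, and then against the other planned outputs.

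**Transitions.** With direction there are five states: low CS, low NCS, normal, high NCS, high CS (CS = clinically significant, NCS = not clinically significant). That gives 5 x 5 = 25 transitions. The SAP scheme has 3 states and 3 x 3 = 9 cells:

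- Abnormal to abnormal: 4 x 4 = 16 transitions in 2 x 2 = 4 cells, so each cell mixes low-to-low, low-to-high, high-to-low and high-to-high.
- Abnormal to normal: 4 transitions in 2 cells, so low-to-normal and high-to-normal are merged.
- Normal to abnormal: 4 transitions in 2 cells, so a fall and a rise are merged.
- Normal to normal: 1 transition in 1 cell.
- Total: 16 + 4 + 4 + 1 = 25.

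Of the 2 x 2 = 4 low-to-high transitions, 2 keep the same grade (low NCS to high NCS, low CS to high CS) and fall on the diagonal, where they read as unchanged. The other 2 fall off the diagonal and read as a change of grade. None shows direction.

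**Study definition against normal range.** The protocol defines iron deficiency as ferritin <100 ng/mL, or 100 to 299 ng/mL with TSAT <20%. Ferritin up to 299 ng/mL can therefore qualify, and ferritin <100 ng/mL qualifies at any TSAT. A subject may be deficient by protocol yet inside the local normal range for one or both markers. For such a subject a rise above the range shows as normal to abnormal, which is visible as a shift but still undirected.

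**What the other planned outputs give.**

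- Tables 14.4.3.1.1 and 14.4.3.1.3 summarise value and change by visit, with mean, median, SD, quartiles, minimum and maximum (SAP 4.2.1). These show the group-level rise and the extremes. They bound a proportion only where a quartile happens to fall: Q1 above 299 ng/mL, for example, would mean that at least 75% of subjects with a value were no longer deficient.
- They do not give the joint definition. If p is the share with ferritin 100 to 299 ng/mL and q the share with TSAT <20%, the share with both lies anywhere from max(0, p + q - 1) to min(p, q).
- Week 12 and Week 24 dosing depends on persisting deficiency, and doses are summarised by visit (SAP 4.8.1, Table 14.1.10.2). Hb limits, pregnancy tests, missed doses and withdrawals also determine dosing, and nothing is given at Week 52.
- Drug-related haemosiderosis and iron-overload events are tabulated (SAP 4.8.2, Table 14.3.1.17), but only those judged related.
- Listings 14.3.4 and 16.2.8.1 hold the individual values, without counts.

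None of these gives n (%) by arm and visit for protocol-defined deficiency or for ferritin >=300 ng/mL.

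**The case against.** The strongest reply is that the information is largely there. Correction of iron deficiency is neither an objective nor an efficacy endpoint, laboratory data are descriptive, and Protocol 12.8 asks only for shift tables, which the SAP supplies. The by-visit summaries would show a rise under treatment, the maximum would show overshoot, and dosing at Weeks 12 and 24 is a rough proxy for persisting deficiency. Because eligibility caps ferritin at 299 ng/mL, an abnormal baseline ferritin is probably low, so abnormal to normal can mostly be read as repletion. That is less secure for TSAT.

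Most of this stands, and it rules out two stronger readings. A reader might infer that every low-to-high move is tabulated as unchanged. The documents do not support that: a change of grade moves the subject off the diagonal, and some subjects may start in the normal range. A reader might also infer that the trial could not show a response in iron status from its planned outputs. At group level it could.

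It is also fair that the SAP's bands would not by themselves reveal excess. TSAT <20% / >=20% has no upper band. Ferritin >=300 ng/mL is the edge of the deficiency definition, and neither document calls it overload.

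What the reply does not answer is the missing counts, or why phosphorus has a banded shift table and the iron markers do not.

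**Conclusion.** The point holds as a minor weakness in descriptive safety reporting. The ferritin and TSAT shift tables merge opposite directions: all 4 low-to-high transitions lose their direction, and 2 of the 4 look unchanged. Counts of subjects by arm and visit who remain deficient by protocol, or who reach ferritin >=300 ng/mL, are absent from the planned tables.

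How many subjects this would affect cannot be worked out, because the documents give neither the local normal ranges nor the expected frequency of such shifts. That the grade is assigned with knowledge of the arm is inferred from Protocol 6.2 and 9.2.3.11; neither document says explicitly who assigns it. The primary analysis, power and type I error are untouched.

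**What to change.** Keep Tables 14.4.3.2.1 and 14.4.3.2.3. In SAP 4.8.5 and the list in 7.1, add:

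1. Value-banded shift tables from baseline to each visit, as for phosphorus, on the SAP 4.5.2 bands: ferritin <100, 100-<300, >=300 ng/mL (3 x 3 = 9 cells) and TSAT <20%, >=20%. Add an upper TSAT band fixed before unblinding (also 3 x 3 = 9 cells). If wanted, add a further upper ferritin band, so that values just past 300 ng/mL are not pooled with much higher ones. The sponsor should choose and justify these limits.
2. One row per visit and arm with n (%) meeting the protocol definition of iron deficiency. Derive it from the definition itself, whose upper bound is 299 ng/mL, not from the <300 band. State the denominator as subjects with the values needed at that visit, since Visit 6 may be held remotely.

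The values are already collected, and deficiency status is already derived for the planned-dose algorithm in Appendix II. The cost is SAP wording, table shells and a little programming.
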